## 14 ETHICAL AND REGULATORY CONSIDERATIONS

### 14.1 IRB/EC Approval

Investigators or designees must submit the study protocol, Informed Consent Forms (if applicable), and all other locally required documentation to an appropriate IRB/EC and obtain study-specific written approval (favorable opinion) before being allowed to participate in the study. Before commencement of the study, the Investigator or designee must provide the Sponsor with written documentation of such approval. The IRB/EC must give written renewal of the original approval at least annually to continue the study, if applicable per local regulation. In this case, a copy of the written renewal must be provided to the Sponsor.

The IRB/EC will be notified of any amendments to the protocol, as well as possible associated information and consent form changes, where applicable, and written approval (favorable opinion) will be obtained prior to implementation, as applicable.

The Investigator or designee is responsible for fulfilling any conditions of approval imposed by the IRB/EC, such as regular safety reporting, study timing, etc. The Investigator or designee will provide the Sponsor with copies of such reports.

### 14.2 Informed Consent and Confidentiality

Prior to any study procedure, the Investigator (or designee) must explain to each participant in layman's terms, the nature of the study, its purpose, expected duration, and the risks and benefits of study participation. For participants under the age of 18, participants' parent(s)/guardian must provide their informed consent and the child must provide assent, depending on local EC requirements, by personally signing and dating the respective consent form prior to begin of this study. For adult participants, where the participant is not able to or not capable to give informed consent, the legal representative will be asked to give consent on behalf of the participant. However, the participant will also be informed about the study within his/her ability to understand.

The Informed Consent process has to be documented in the participant's medical records. Also, participant will be informed of uses and disclosures of their medical information for research purposes, and their rights to access information about them. All applicable national privacy laws (e.g., General Data Protection Regulation [GDPR] requirements in the EU) will be followed in this study. The participants must be informed of their right to withdraw from the study at any time and for any reason without sanction, penalty, or loss of benefits to which they are otherwise entitled, and that withdrawal from the study will not jeopardize their future medical care. Participants will be informed of their right to new information and/or findings relating to the clinical study, and the process by which this information is made available. After this explanation, given sufficient time to decide whether to participate, before any study procedure is conducted, and before entering the study, the participant must voluntarily provide consent by signing and dating the form personally in accordance with ISO 14155: 2020(E). The participant will receive a copy of

his/her signed ICF. If new information becomes available that may significantly affect the subject's health status, then this information will be provided in written form. Re-consent will be obtained if this is considered as necessary.

The above requirements also apply with respect to informed consent obtained from participant's legally designated representative.

#### **14.2.1 Confidentiality**

Participant confidentiality must be strictly held in trust by the Investigator, study staff, and the Sponsor. Participant confidentiality and anonymity will be maintained by removal of identifiers from any data, documentation, or clinical samples submitted to the Sponsor.

Any data collected meeting the definition of protected/confidential health information or personal identifying information will be collected and maintained using the designated authorizations and following privacy procedures as specified in the applicable regulatory authority regulations including the EU GDPR.

The Sponsor-Monitor, authorized representatives of the sponsor, and/or applicable Health Authorities may inspect all documents and records required to be maintained by the Investigator. The Investigator/Site will permit access to such records.

#### **14.3 Regulatory Status**

The study device is CE marked and will be studied in a post-market fashion in Europe.

#### **14.4 Statement of Compliance**

This clinical investigation will be conducted in compliance with the protocol and following regulatory requirements:

- ISO14155:2020 (Good Clinical Practice);
- EU MDR (Council Regulation 2017/745 of 5 April 2017);
- Ethical principles of the Declaration of Helsinki, in its current revision; and
- Applicable sections of the national laws and regulations.

The clinical investigation will not commence at a clinical site until approval (favorable opinion) from the respective IRB/EC has been received. All additional requirements imposed by the IRB/EC(s) will be followed. Involvement of the national competent authorities (e.g. by notification, seeking authorization) will be accomplished as required by national laws and regulations.

CV	Curriculum Vitae
DEHP	Diethylhexyl Phthalate
DMP	Data Management Plan
EDC	Electronic Data Capture
EEA	European Economic Area
EU	European Union
FDA	Food and Drug Administration
FDAAA	FDA Amendments Act of 2007
GCP	Good Clinical Practice
GDPR	General Data Protection Regulation
ICF	Informed Consent Form
ICH	International Conference on Harmonisation
ICMJE	International Committee of Medical Journal Editors
IFU	Instructions for Use
IPA	Isopropyl Alcohol
IRB/EC	Institutional or Independent Review Board/Ethics Committee
IV	Intravenous
NDA	Non-disclosure Agreement
PI	Principal Investigator
SADE	Serious Adverse Device Effect
SAE	Serious Adverse Event
SIV	Site Initiation Visit
TMF	Trial Master File
UADE	Unexpected Adverse Device Effect
USADE	Unexpected Serious Adverse Device Effect
VAD	Vascular Access Device

1 Introduction

1.1 Background and Rationale

This study is designed to provide data utilizing the Becton Dickinson (BD) PureHub™ Disinfecting Cap for the purpose of providing clinical data required under European Union (EU) regulation 2017/745.

1.2 Objectives and Endpoints

Objectives	Endpoints
Primary Efficacy Objective	
To assess the rate of select performance measures of the BD PureHub™ Disinfecting Caps on swabbable needle-free connectors when used in a clinical environment.	
 ▪ Attachment success rate of the BD PureHub™ Disinfecting Caps to a needle-free connector (successful attachment/ total number of attachments) ▪ Removal success rate of the BD PureHub™ Disinfecting Caps to a needle-free connector (successful removal/ total number of intended removals)
Primary Safety Objective	
To assess the incidence of BD PureHub™ Disinfecting Cap device-related adverse events.	
 ▪ Rate of device-related adverse events
Informative Objectives	
To assess the frequency of BD PureHub™ Disinfecting Cap use To summarize the purposes for removal of the BD PureHub™ Disinfecting Cap from the needle-free connector To summarize the incidence of blood stream infection	
 ▪ The number of BD PureHub™ Disinfecting Caps used per day/per study participant ▪ The purpose for each intended removal of the BD PureHub™ Disinfecting Cap from the needle-free connector ▪ Incidence of central line associated bloodstream infection (CLABSI) ▪ Incidence of bloodstream infections

2 Study Description

2.1 Study Design

This is a multi-center, single-arm, prospective post-market study that will enroll up to 175 participants in order to have 150 evaluable participants who have vascular access devices as part of their routine medical care. Data related to the safety and performance of the BD PureHub™ Disinfecting Cap will be captured when used as intended.

Participants will be screened against eligibility criteria and will be considered enrolled once the informed consent document is signed. Each study participant will have a BD PureHub™ Disinfecting Cap attached to each eligible needle-free connector to one or more VADs by a clinician. Clinicians will then be advised to place subsequent BD PureHub™ Disinfecting Caps as per the Instructions for Use through the course of the participant's IV therapy. During this time, attachment and removal success will be captured, as well as any device-related adverse events (AEs).

Participants will be followed from the time of enrollment until one week post VAD therapy, department/hospital discharge or 45 days post enrollment date, whichever comes first. Participants, with a VAD in place, who will be discharged from the hospital, but return regularly for catheter access to the site will remain in the study, either until the 45 days are reached or the VAD therapy is ended. If the catheter access will not be performed at the clinical trial site, the participant cannot continue in the study.

2.2 Study Population

Participants will be recruited from the patient population treated at the investigational sites. The inclusion/exclusion criteria are described in the protocol Section 5.

2.3 Randomization and Blinding

This is a single-arm study and randomization is not applicable.

2.4 Sample Size

Assuming the primary endpoints of successful insertion rate and successful removal rate are each 90%, a sample size of 150 participants with only 1 insertion/removal observed per participant would result in a 4.8% precision for each point estimate (i.e., the 95% confidence interval is the point estimate $\pm 4.8\%$, using a simple asymptotic approach for confidence interval of one proportion). The precision margin will tighten as the number of line access per participant increases, for example, with an average of 4 insertions/removals per participant, the precision would be $\pm 2.4\%$.

Additionally, with a sample size of 150, the probability of observing at least one rare AE/complication with a 1% rate (per participant) is 78% and the probability of observing at least one rare AE/complication with a 2% rate (per participant) is 95%.

2.5 Interim Analyses

No interim analysis is planned for the study.

2.6 Study Procedure

Participants will be screened against eligibility criteria and will be considered enrolled once the informed consent document is signed. Each study participant will have a BD PureHub™ Disinfecting Cap attached to each eligible needle-free connector to one or more VADs by a clinician. Clinicians will then be advised to place subsequent BD PureHub™ Disinfecting Caps as per the Instructions for Use through the course of the participant's IV therapy. During this time, attachment and removal success will be captured, as well as any device-related adverse events (AEs).

Participants will be followed from the time of enrollment until one week post VAD therapy, department/hospital discharge or 45 days post enrollment date, whichever comes first. Participants, with a VAD in place, who will be

discharged from the hospital, but return regularly for catheter access to the site will remain in the study, either until the 45 days are reached or the VAD therapy is ended. If the catheter access will not be performed at the clinical trial site, the participant cannot continue in the study.

2.7 Endpoints

Refer to Section 1.2.

2.8 Acceptance Criteria

There are no acceptance criteria for the study device.

3 Intended Statistical Software and Data Information

3.1 Intended Statistical Software

All the analyses will be performed using Statistical Analysis System (SAS) Version 9.4 or above or R.

3.2 Data Information

Derived data specification will be finalized prior to reporting.

4 Analysis Population Set(s)

4.1 Population Definitions

Enrolled: All participants who sign the ICF.

Evaluable: All enrolled participants who have at least 1 BD PureHub™ Disinfecting Cap applied.

5 Statistical Analysis/Calculations

5.1 Primary Performance Endpoints

The primary performance endpoints are:

- Attachment success rate of the BD PureHub™ Disinfecting Caps to a needle-free connector
- Removal success rate of the BD PureHub™ Disinfecting Caps to a needle-free connector

The attachment success will be performed on enrolled population with non-missing data on PureHub Initial Placement CRF page. The removal success will be performed on evaluable population.

If the clinician can successfully attach the first BD PureHub™ Disinfecting Cap, it is considered as attachment success. Attachment success will be based on count of “Yes” responses to the following fields in the CRF pages:

- PureHub Initial Placement page, Attachment success is “Yes”
- PureHub Maintenance page, Attachment success is “Yes”

The attachment success rate will be computed as the number of successful attachments divided by the total number of attachments. The total number of attachments can be calculated using the following CRF pages:

- PureHub Initial Placement page, Attachment success is “Yes” or “No”

- PureHub Maintenance page, Attachment success is “Yes” or “No”.

The removal success rate will be computed as the number of successful removals divided by the total number of removals.

Removal success will be based on counts of “Yes” response to “Removal success” question in the “PureHub Maintenance” CRF page. Total number of intended removals will be based on the number of times the “Removal Success” response is chosen (regardless of “Yes” or “No”).

95% confidence interval will be calculated for both rates using the Clopper-Pearson exact method.

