## Schema

*Table 1 – Schedule of activities*

Procedure/Assessment	Baseline	Initial PureHub Placement  Day 0	Each day during VAD Therapy 	7-day Follow Up after VAD Therapy 	End-of-study 45-day FU or Department/ Hospital Discharge, whichever comes first 
Informed consent process, incl. Informed consent signature date	X				
Inclusion/Exclusion Criteria Check	X				
Patient in-hospital location information	X	(X) 	(X) 	(X) 	
Demographics	X				
Medical History	X				
VAD Information 	X	(X) 	X		
BD PureHub™ Placement Record number of eligible needle-free connectors per VAD • Placement of PureHub™ Caps • Record number of new caps used and location catheter line per day incl. primary reason for cap replacement • Document Yes or No if able to successfully attach a PureHub™ Disinfecting Cap per needle-free connector for each attachment. • Document number of attachments • Document Yes or No if able to successfully remove the BD PureHub™ Disinfecting Cap from the needle-free connector • Document number of intended removals		X	X		X
Device related Adverse Events assessment		X	X	X	X
Blood stream infection assessment		X	X	X	X
Device deficiency assessment		X	X		

- 1) Initial PureHub™ Placement can be performed on same day as Baseline, provided ICF has been signed.
- 2) Multiple Placements of PureHub™ Caps are possible per day
- 3) VAD Information: At baseline -VAD type, number of VADs, number of lumens per catheter, location of VADs, date of VAD placement, type and number of needle-free connectors per VAD, type of dressing; subsequent visits; type of dressing in case of changes, dressing changes, needle-free connector changes,
- 4) Only applicable for patients who continue to be hospitalized at the department/hospital and continue study participation
- 5) End of study is also applicable if the patient is discharged from department and cannot be followed up by the clinical investigation team at another department/ward
- 6) Baseline VAD Information at initial PureHub™ Placement day needs to be reconfirmed if the visit date is different to baseline date
- 7) Only in case participant is transferred to another department/ward and continues in the study, or participant is discharged home in-between hospital visits but the VAD is still in place.

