## 7.5 Efficacy (Performance) Assessment

Clinicians will be requested to document the following with each use of the BD PureHub™ Disinfecting Cap:

- Attachment success: The clinician will document if able to successfully attach the BD PureHub™ Disinfecting Cap to each of the applicable needle-free connectors securely. (Documenting either “Yes” or “No”).
  - An *attachment* is defined as the process of placing a PureHub™ Disinfecting Cap on an eligible needle-free connector.
  - If the clinician can successfully attach the first BD PureHub™ Disinfecting Cap, they should document “Yes” as this would be an attachment success. Attachment success means the cap is securely attached to the needle-free connector and that the needle-free luer is connected.
  - If the clinician is unable to successfully attach the cap to the needle-free connector, they should use a new subsequent BD PureHub™ Disinfecting Cap. The answer to attachment success would be “No” as more than one cap was needed to reach attachment success. The number of subsequent caps needed to achieve a successful attachment during this procedure need to be documented.

If the clinician is unable to attach the cap to the needle-free connector with any subsequent caps, they should document the number of subsequent caps used and document “Unable to attach.”

- Removal success: The clinician will document if able to successfully remove the BD PureHub™ Disinfecting Cap from the needle-free connector (Yes/No).
  - An *intended removal* is defined as the process of removing a successfully attached PureHub™ Disinfecting Cap from an eligible needle-free connector for the purpose of access to the needle-free connector or to replace with a new PureHub™ Disinfecting Cap.

If the clinician can remove the PureHub™ Disinfecting Cap from the needle-free connector, they should document “Yes” as this would be a removal success.

If the clinician cannot remove the PureHub™ Disinfecting Cap from the needle-free connector, they should document “No”.

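### Does the attachment success rate lose the connectors on which no cap could be attached?

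*SAP*

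**What the plan says.** **The outcomes in Protocol 7.5.**
- If the first cap attaches, the answer is *Yes*.
- If it does not, a new cap is used and the answer is *No*, explained by the words "as more than one cap was needed to reach attachment success".
- If no later cap attaches either, "they should document the number of subsequent caps used and document “Unable to attach".

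The same section opens the item with "Documenting either “Yes” or “No". It says that an attachment "is defined as the process of placing a PureHub™ Disinfecting Cap on an eligible needle-free connector", a definition that does not depend on the result.

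**The schedule of activities (Protocol Table 1).** The instruction is "Document Yes or No if able to successfully attach a PureHub™ Disinfecting Cap per needle-free connector for each attachment".

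**SAP 5.1.** The numerator is the count of *Yes*. The denominator is taken from "PureHub Initial Placement page, Attachment success is “Yes” or “No" and the matching Maintenance field. *Unable to attach* is not mentioned. The removal denominator is worded differently: it is "based on the number of times the “Removal Success” response is chosen (regardless of “Yes” or “No".

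**Elsewhere in the SAP.** Section 3.2 leaves derived-data rules to a specification to be finalized before reporting. Section 2.8 states: "There are no acceptance criteria for the study device".

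**The concern.** Protocol 7.5 names three entries and SAP 5.1 counts two. The reason given for *No* describes a connector that took a cap in the end, so it fits poorly where no cap ever went on. A reader could conclude that *Unable to attach* is a third value that stands in place of *No*. The SAP's two-value list, applied literally, would then drop exactly the records in which the device failed completely.

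Such an exclusion depends on the outcome and works in one direction only. With no hypothesis test and no acceptance criterion, the estimate and its confidence interval are what the study delivers, so an inflated primary rate would matter.

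**Working it through.** **1. Follow one total failure through the plan.**
- The clinician tries the first cap and it does not attach. Under Protocol 7.5 the answer to attachment success is now *No*.
- Further caps are tried and fail. The clinician records how many were used and writes *Unable to attach*. Nothing tells the clinician to withdraw the *No*.
- Protocol Table 1 requires a *Yes* or *No* for each attachment and makes no exception, so the field is still to be filled.
- SAP 5.1 finds *No*, adds one to the denominator and nothing to the numerator. The failure is counted.

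On this path *Unable to attach* sits beside the cap count as a note on what happened after the first cap. It parallels the instruction just before it in Protocol 7.5, to record how many further caps were needed. The SAP's two values then cover every attachment.

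**2. Does the removal wording show a deliberate contrast?** The removal rule also names only *Yes* and *No*, and removal is a plain two-value item in Protocol 7.5. The different phrasing does not show that attachments have an excluded third category.

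**3. Reproduce the plan's precision figures.** The inputs from SAP 2.4 are a 90% rate, 150 participants, and 1 or 4 attachments each. The half-width is 1.96 × √(p(1 − p)/n), treating attachments as independent as the plan does.
- n = 150: 1.96 × √(0.9 × 0.1/150) = 4.8 points.
- n = 150 × 4 = 600: 1.96 × √(0.9 × 0.1/600) = 2.4 points.

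Both agree with the SAP.

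**4. Size under the less natural reading.** Let S be the *Yes* records, F all failures, and U the failures entered only as *Unable to attach*. The intended rate is S/(S + F). The literal rule would give S/(S + F − U), which is higher whenever U > 0 and S > 0. Take 600 attachments with S = 540 and F = 60. The share U/F is not in the documents, so the values below are assumptions.

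| Assumed share of failures | U | Rate | Exact 95% CI | Shift (points) |
|---|---|---|---|---|
| 0% | 0 | 540/600 = 90.0% | 87.3 to 92.3 | 0 |
| 10% | 6 | 540/594 = 90.9% | 88.3 to 93.1 | 0.9 |
| 25% | 15 | 540/585 = 92.3% | 89.8 to 94.3 | 2.3 |
| 50% | 30 | 540/570 = 94.7% | 92.6 to 96.4 | 4.7 |

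The shift reaches the 2.4-point half-width when 540/(600 − U) = 0.924. That gives U = 600 − 540/0.924 = 15.6, or about 26% of the 60 failures. If the true rate were 98% (588 *Yes*, 12 failures, also an assumption), shares of 25% and 50% would give 588/597 = 98.5% and 588/594 = 99.0%.

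The top row is the result when the plan is followed as in step 1. The other rows need the form to record *Unable to attach* in place of *No*, which nothing in the documents shows.

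**The case for a change.** The strongest case for a change is that no sentence in either document maps *Unable to attach* to *No*. The protocol introduces it with the same verb and quotation marks as the other two answers, and the stated reason for *No* presumes eventual success. The rest of the plan shows that failed attempts are meant to count:
- SAP 5.1 analyses attachment in enrolled participants with Initial Placement data, not only in those who had a cap applied.
- SAP 5.3 includes caps that were tried but did not attach when it counts caps per day.

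A blank *Yes*/*No* field could also remove a participant through the non-missing-data condition in SAP 5.1. One sentence would close the matter.

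Part of this stands. The rule is unwritten, the reason given for *No* is loosely worded, and the direction of any error is certain. However, the evidence of intent also tells an analyst how to score the entry: an attachment is the act of placing a cap, and success means that the first cap went on. An analyst who met a stand-alone *Unable to attach* would have no basis in the plan for treating it as anything but a failed attachment. A blank field would contradict the instruction in Protocol Table 1, so it would be a matter for a data query.

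**Conclusion.** No change to the plan is needed. Followed as written, the protocol puts a *No* on record before *Unable to attach* can arise, SAP 5.1 counts that *No*, and the attachment rate is unbiased. What is missing is a field-level coding statement, which belongs in the derived data specification that SAP 3.2 provides for and which analysts would settle in the obvious way.

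The shifts of 0.9 to 4.7 points at a 90% rate are conditional on two things that the documents do not supply: a form that enters *Unable to attach* instead of *No*, and an assumed share of failures of that kind. The largest shift needs half of all failures to be connectors that no cap would fit. At an assumed true rate of 98% the same shares move the estimate by 0.5 to 1.0 point. Because SAP 2.8 sets no acceptance criteria, no pass or fail decision depends on the point.

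The conclusion rests on reading the attachment field as two-valued, as Protocol 7.5, Protocol Table 1 and SAP 5.1 all describe it. The case report form is not among the documents, so its layout could not be checked.

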## 4 STUDY DESIGN

### 4.1 Overall Design

This is a multi-center, single-arm, prospective post-market study that will enroll up to 175 participants in order to have 150 evaluable participants who have vascular access devices as part of their routine medical care. Data related to the safety and performance of the BD PureHub™ Disinfecting Cap will be captured when used as intended.

Participants will be screened against eligibility criteria and will be considered enrolled once the informed consent document is signed. Each study participant will have a BD PureHub™ Disinfecting Cap attached to each eligible needle-free connector to one or more VADs by a clinician. Clinicians will then be advised to place subsequent BD PureHub™ Disinfecting Caps as per the Instructions for Use through the course of the participant's IV therapy. During this time, attachment and removal success will be captured, as well as any device-related adverse events (AEs).

Participants will be followed from the time of enrollment until one week post VAD therapy, department/hospital discharge or 45 days post enrollment date, whichever comes first. Participants, with a VAD in place, who will be discharged from the hospital, but return regularly for catheter access to the site will remain in the study, either until the 45 days are reached or the VAD therapy is ended. If the catheter access will not be performed at the clinical trial site, the participant cannot continue in the study.

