### 4.3 End of Study Definition

A participant is considered to have completed the study when one of the following conditions are met, whichever is the earliest.:

- upon one week post VAD therapy (after the last VAD is removed),
- at department discharge provided the clinical investigation team cannot follow-up the participant on another ward for study purposes,
- at hospital discharge provided participant, if VAD is still placed, will not return for catheter access to the site or,
- 45 days from enrollment

If a participant has more than one (1) VAD with eligible needle-free connectors at study start, data will be collected on each VAD and the end of study time point occurs when the last VAD is removed. If an additional VAD is placed at a later time point, or if one of these VADs is replaced, then the new VAD is excluded from the study.

The end of the study is defined as the date of the last study assessment of the last participant in the study.

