### 6.3 Ancillary Devices/Products

Ancillary devices will include the participant's VAD, eligible needle-free luer connectors, intravenous tubing, and dressings, or any other material associated with the participant venous access. These products will be used as part of the standard of care of each site. Selected information regarding these devices will be collected (See Section 7.7). The use of other disinfecting caps than the PureHub™ disinfecting cap is not allowed.

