## 7.4 Device Use

Each study participant will have a BD PureHub™ Disinfecting Cap attached to each eligible needle-free connector by a clinician. “Eligible” needle-free connector will be defined as a swabbable needle-free connector not already in use and is reasonably able to be accessed by a clinician.

Clinicians should place subsequent BD PureHub™ Disinfecting Caps as per the Instructions for Use. Lot numbers of the PureHub™ devices will be documented in the eCRF.

Clinicians will be advised to follow the respective unit protocol for disinfection of needle-free luer connectors prior to initial access.

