### 10.2 Sample Size Considerations

Assuming the primary endpoints of successful insertion rate and successful removal rate are each 90%, a sample size of 150 participants with only 1 insertion/removal observed per participant would result in a 4.8% precision for each point estimate (i.e. the 95% confidence interval (CI) is the point estimate  $\pm 4.8\%$ , using a simple asymptotic approach for CI of one proportion). The precision margin will tighten as the number of line access per participant increases, for example, with an average of 4 insertions/removals per participant, the precision would be  $\pm 2.4\%$ .

Additionally, with a sample size of 150, the probability of observing at least one rare AE/complication with a 1% rate (per participant) is 78% and the probability of observing at least one rare AE/complication with a 2% rate (per participant) is 95%.

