### 10.4 Primary Performance Endpoints

The attachment (removal) success rate will be calculated by dividing the number of successful attachment (removal) by the total number of attachments (removals); 95% CI will be calculated using a score method.

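### The confidence intervals for attachment and removal success treat repeated events in one participant as independent, and so does the stated ±2.4% precision

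*SAP*

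**What the plan says.** SAP 5.1 defines attachment success as all Yes answers over all Yes or No answers on the Initial Placement and Maintenance pages. It defines removal success the same way from the Maintenance page. It then says "95% confidence interval will be calculated for both rates using the Clopper-Pearson exact method". Protocol 10.4 uses the same event-level rates, dividing "by the total number of attachments (removals); 95% CI will be calculated using a score method".

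The design produces repeated events per person:

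- Protocol 7.4: "Each study participant will have a BD PureHub™ Disinfecting Cap attached to each eligible needle-free connector by a clinician".
- Protocol 4.3: "If a participant has more than one (1) VAD with eligible needle-free connectors at study start, data will be collected on each VAD".
- Protocol Table 1, footnote 2, allows several placements in a day, and Protocol 7.5 asks for documentation at each use.
- Protocol 4.1 ends follow-up at the earliest of one week after VAD therapy, "department/hospital discharge or 45 days post enrollment date, whichever comes first".

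On precision, Protocol 10.2 says "The precision margin will tighten as the number of line access per participant increases". SAP 2.4 adds that "with an average of 4 insertions/removals per participant, the precision would be" ±2.4%, against ±4.8% with one event each.

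The supplied text has no adjustment for repeated events. Protocol 10.7 (Other Analyses) is marked not applicable. The table shells in SAP Appendix 1 are not visible.

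**The concern.** Clopper-Pearson and score intervals are built for independent trials with one common success probability. Here the trials come in groups, one group per participant. If some participants are persistently harder to cap or uncap than others, the pooled count varies more than a binomial count does, and the nominal 95% interval covers less than 95%.

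The documents neither give an ICC nor argue that it is zero. Each placement uses a new cap, so defects of the cap itself may be nearly independent. Repeated events can, however, fall on the same connectors of the same participant. On connectors and other ancillary products, Protocol 6.3 says: "These products will be used as part of the standard of care of each site". If success depends on how cap and connector fit, it will tend to repeat within a person. The number of events per person is also likely to differ, because the number of VADs, the number of connectors and the length of follow-up all differ. Unequal counts make the problem larger.

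This is a single-arm estimation study without a test, so its performance result is two rates with their intervals. An interval that is too narrow misstates how well those rates are known.

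**Working it through.** **Inputs from the documents** (Protocol 10.2, SAP 2.4): 150 participants, success rate p = 0.90, 95% confidence, simple asymptotic interval, 1 or 4 events per participant. Every ICC, and every event count other than 1 and 4, is an assumption.

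**Step 1: reproduce the plan's figures.** The half-width is 1.96 × √(p(1 − p)/n).

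- n = 150: 1.96 × √(0.09/150) = 4.80%.
- n = 150 × 4 = 600: 1.96 × √(0.09/600) = 2.40%.

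Both match. The second needs 600 independent observations, that is, ICC = 0.

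**Step 2: allow for correlation.** With m equal events per participant the variance is multiplied by the design effect 1 + (m − 1) × ICC. For m = 4:

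| ICC (assumed) | Design effect | Effective n | Half-width |
|---|---|---|---|
| 0 | 1.00 | 600 | ±2.40% |
| 0.05 | 1.15 | 522 | ±2.57% |
| 0.1 | 1.30 | 462 | ±2.74% |
| 0.3 | 1.90 | 316 | ±3.31% |
| 1 | 4.00 | 150 | ±4.80% |

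The figure still rounds to ±2.4% while the half-width is below 2.45%. That is up to a design effect of (2.45/2.4005)² = 1.0417, or ICC 0.0417/3 = 0.0139.

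**Step 3: unequal counts.** In the design effect, m is replaced by Σmᵢ²/Σmᵢ, where mᵢ is participant i's event count. Take geometric counts starting at 1 with mean 4. Their variance is 12, so the ratio is (12 + 16)/4 = 7. At ICC 0.1 the design effect is 1 + 6 × 0.1 = 1.6 instead of 1.3, and the half-width is 2.40 × √1.6 = 3.04%.

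**Step 4: coverage of the planned 95% intervals.** Beta-binomial simulation, 150 participants, p = 0.90, 20,000 runs per setting:

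| Events per participant | Interval | ICC 0.05 | ICC 0.1 | ICC 0.3 |
|---|---|---|---|---|
| 4, equal | Clopper-Pearson | 94.2% | 92.6% | 85.9% |
| 4, equal | score | 93.6% | 91.9% | 84.6% |
| mean 4, geometric | Clopper-Pearson | 92.6% | 89.0% | 77.5% |
| 10, equal | Clopper-Pearson | 90.1% | 85.0% | 69.4% |
| 20, equal | Clopper-Pearson | 84.8% | 76.4% | 56.5% |

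At ICC 0 with 4 equal events, Clopper-Pearson covers 96.1% and score 95.3%. Repeat runs with other seeds agree within about one percentage point.

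**Step 5: success rates nearer 100%** (10,000 runs). With 4 equal events at ICC 0.05 and 0.1, pooled Clopper-Pearson covers 95.0% and 93.3% at p = 0.99, and 98.2% and 97.4% at p = 0.995. With 20 equal events at ICC 0.1 it covers 76% to 78% at p = 0.90, 0.99 and 0.995 alike.

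**The case against.** The strongest reply is that the harm is conditional and no decision rests on it. SAP 2.8 sets no acceptance criterion, and there is no hypothesis test and no control arm. The point estimates and the participant-level safety interval do not change. The choice of 150 participants is first justified with one event each, ±4.8%. For 4 equal events that is also the worst case, so the sample size does not depend on ±2.4%, which is only an illustration. At ICC 0.05 with 4 equal events the SAP interval still covers about 94%. With few events and a success rate near 100%, Clopper-Pearson is close to nominal or conservative (step 5). The large losses need 10 to 20 events per participant or an ICC near 0.3, and neither figure is in the documents.

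All of that stands, and it limits the seriousness of the point. It does not rescue the method. Zero correlation is assumed without a reason. Several connectors, several placements a day and follow-up of up to 45 days can take counts well above 4. At 20 events and ICC 0.1 a high success rate gives no protection.

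Two further points also stand. Connector type set by site practice would cause correlation within site as well, and clustering on participant does not capture that. The unseen shells might show an adjustment, but the SAP text names the method plainly.

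**Conclusion.** The concern holds. Both documents apply independent-trial intervals to pooled repeated events, and ±2.4% is correct only at an ICC of essentially zero (below about 0.014, with equal counts). With positive within-participant correlation the planned intervals are too narrow. The extent depends on two quantities that the documents do not give: the ICC and the distribution of events per participant. For the plan's own example the range runs from negligible (ICC 0.05 or less, 4 equal events) to a half-width twice the stated one (ICC 1). The point should be fixed because these intervals are the performance result. It does not threaten the point estimates, the safety analysis or the choice of 150 participants.

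**What to change.** **SAP 5.1 and Protocol 10.4.** Keep the pooled rates. Name one confidence interval method with participant as the cluster, the same in both documents; at present they name different methods. Any standard participant-clustered method will do. One example is Clopper-Pearson on an effective sample size N/max(1, D). Here N is the number of events and D is the participant-cluster-robust (ratio-estimator) variance divided by p(1 − p)/N.

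**Few failures.** Fix a rule before database lock, because D is undefined or unstable when failures are rare. For example, set D = 1 with zero failures. When fewer than 10 participants have a failure, add a sensitivity interval on N/max(D, 1 + (Σmᵢ²/Σmᵢ − 1) × ρ₀), with ρ₀ stated in advance, say 0.1. With 150 × 4 events the lower limits are:

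| Failures | Main | Sensitivity |
|---|---|---|
| 0 | 99.39% | 99.20% |
| 1 | 99.07% | 98.89% |
| 2, different participants | 98.80% | 98.60% |
| 2, one participant | 98.15% | 98.15% |

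**Protocol 10.2 and SAP 2.4.** State that with 4 events per participant the half-width lies between ±2.4% (no within-participant correlation) and ±4.8% (complete correlation), for example ±2.7% at ICC 0.1, and is wider with unequal counts. State also that correlation within site and within clinician is not covered.

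**Cost.** A SAP amendment and a few lines of code, with no extra data or participants. Protocol 10 leaves technical detail to the SAP. Changing Protocol 10.2 and 10.4 is a protocol amendment, handled with the ethics committee under Protocol 14.1. If the ICC is really 0, the example interval costs little at p = 0.90: mean half-width 2.53 against 2.48 points with 4 equal events, and 1.11 against 1.09 with 20. At p = 0.90 it covers 94.3% to 96.2% across the 30 settings tried (ICC 0 to 0.3).

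**Limits of the example.** Near 100% success the main interval can still under-cover. At p = 0.99, ICC 0.3 and 20 equal events it covers about 91%, against 56% for the pooled interval; with geometric counts averaging 20 it covers 86% against 45%. The sensitivity interval covers 93.0% and 94.7% in those two settings if computed in every run. The threshold of 10 would print it in only about 66% and 82% of runs, so printing it always is safer. Its price shows when the ICC is 0: at p = 0.99 with 20 equal events its half-width is 0.66 points against 0.38.
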